### **Number of patients who are adherent to WHO Guidelines for the definition of physical activity**

Number and proportion along with the 95%CI (Clopper-Pearson's formula) of subjects who are adherent to World Health Organization Guidelines for the definition of physical activity will be calculated in the whole sample and compared by age group.

Adherence to WHO guidelines will also be summarized:

- by start of any newly approved drug for haemophilia (see Section 4.4.4 for subgroup definition).
- by COVID-19 period on the EVL population (see Section 4.4.4 for subgroup definition).
- by month through the entire observational period on the EVL to observe the impact of COVID-19.

The adherence will be summarized considering data collected in each period above-mentioned.

Other subgroup analyzes: severity of the disease (see Section 4.4.4 for subgroup definition).

### **Number, sites and types of bleeds occurring during routine clinical practice and reported at any occurrence via the electronic Patient-Reported Outcome (ePRO) application**

The overall number of bleeds per patients will be analyzed by means of descriptive statistics as described in Section 4. Data will be shown overall and by age group.

Bleeds that occur the same day but in different body site will be counted separately. Number and proportion of patients with no bleeds and 1 or more bleeds will also be shown.

The bleeds will be analyzed overall, by body site (Joint bleeds, Muscle bleeds, Other bleeds) and type (Spontaneous bleeds, Traumatic bleeds, Bleeds related to procedure/surgery).

The 95%CI for the mean number of bleeds will also be shown.

Number, sites and types of bleeds will also be summarized:

- by start of any newly approved drug for haemophilia (see Section 4.4.4 for subgroup definition).
- by COVID-19 period (see Section 4.4.4 for subgroup definition).
- by month through the entire observational period to observe the impact of COVID-19.

Other subgroup analyzes: frequency of physical activity, severity of the disease.

**Treatment regimen for haemophilia A (prophylaxis, preventive treatment before physical activity, treatment for any episode of bleeds), in terms of type of regimen (demand vs. prophylaxis), product used and dose.**

**Treatment regimen for Haemophilia A**

Only concomitant medication for haemophilia will be displayed. Prophylaxis and “on demand” treatment for haemophilia will be summarized separately. Frequency distributions and percentages will be summarized in the Evaluable population by Anatomical Main Group (1st level of the Anatomical Therapeutic Chemical (ATC) classification), Chemical Subgroup (4th level of the ATC classification) and Preferred Name.

Subjects taking more than one medication classified in the same category (prior medications or concomitant medications) within the same anatomical main group, chemical subgroup and preferred name will be counted only once.

Number and proportion of subjects who take prophylaxis and “on demand” treatment for haemophilia during the study will be also shown.

A detailed listing with the concomitant treatments for haemophilia, regimen (prophylaxis, on demand) dose and frequency will be generated.

Moreover, number and proportion of patients who start treatment with any newly approved drugs during the study for prophylaxis treatment in patients with haemophilia A without inhibitors will be presented.

Other subgroup analyzes: frequency of physical activity, severity of the disease, start of any newly approved drug for haemophilia (see Section 4.4.4 for subgroup definition).

**Treatment regimen for bleeding**

The following information collected in the eCRF will be shown to describe the treatment for bleeding:

- number and proportion of treated bleedings
- number and proportion of bleeds treated with each type of treatment for bleeding (haemostatic treatment, treatment for pain)
- duration of treatment for bleed (hours)
- number and proportion of bleeds treated with each route of administration

- number and proportion of bleeds which needed to receive a transfusion
- number and proportion of bleeds which needed to administer an additional hemostatic therapy
- number and proportion of bleeds which with adherence to the treatment regimen in the week preceding the bleeding.

A listing with complete information on each bleed and its treatment will be also provided.

Treatment regimen for bleed will also be analyzed by the intensity of physical activity done in the 2 days preceding the day of bleeding. Intensity of physical activity will be defined considering the MVPA done in the 2 days before the bleeding. MVPA minutes will be summarized as median of the values recorded in the 2 valid days before the bleeding. A median greater than 0 minutes will mean an intense physical activity (in case of only one valid day, that value will be used to summarize the physical activity preceding the bleeding).

Other subgroup analyzes: severity of the disease (see Section 4.4.5 for subgroup definition).

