## 2.2 OUTCOME MEASURES

The co-primary outcome measures are given by the physical activity data collected through a wearable device (i.e., fitness tracker) in terms of active minute, METs and steps count.

According to the protocol (see Study protocol, Section 6.1.1), a valid day of monitoring is defined as at least 10 wearing hours per day. Only data from days in which the fitness tracker was worn for at least 10 hours will be included in the statistical analysis (see Appendix 3 for the derivation of the wearing time).

The minutes are saved in two different sets of data collected by the fitness tracker. For each set, minutes are categorized by intensity of the activity done.

The first set is comprised of the minutes categorized accordingly to the time collected in each heart zones (following referred as “heart zone minutes”):

- fat-burn minutes,
- cardio minutes,
- peak minutes.

The second set is comprised of the minutes categorized accordingly to the active zones (following referred as “active zone minutes”):

- lightly active minutes,
- fairly active minutes,
- very active minutes.

The conversion from heart zones to active zones is not shared by the owner of the fitness tracker but it is known that it is based on the METs (Metabolic Equivalent of Task). The MET is the objective measure of the ratio of the rate at which a person expends energy, relative to the mass of that person, while performing some specific physical activity compared to a reference. METs calculated by the fitness tracker are not directly available but must be derived.

In our analysis, the METs will be derived by using the following formula:

$$1 \text{ MET} = \frac{\text{kcal}}{\text{kg} * \text{h}}$$

where:

- $kcal$  will be given by the sum of calories collected by the fitness tracker during the time spent in fat-burn, cardio and peak heart zones, respectively.
- $kg$  will be given by the weight collected in the eCRF at baseline and every 3 months when the observation visit is conducted and the weigh is collected (the weight is assumed constant between each visit and the subsequent, in case of missing assessment, the last available value will be carried forward).
- $h$  is the time that will be derived as sum of fat-burn minutes, cardio minutes, and peak minutes.

The minutes will be also analyzed in terms of overall sum:

$$\begin{aligned} \text{overall heart zone minutes} &= \\ &= \text{fatburn minutes} + \text{cardio minutes} + \text{peak minutes} \end{aligned}$$

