$$\begin{aligned} \text{overall active minutes} &= \\ &= \text{lightly active minutes} + \text{fairly active minutes} + \text{very active minutes} \end{aligned}$$

And of MVPA (Moderate-to-Vigorous Physical Activity) minutes:

$$\text{MVPA minutes} = \text{fairly active minutes} + \text{very active minutes}$$

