### 2.2.1 Secondary Endpoints

- To document physical activity, particularly in terms of active minutes, by ages categories (12-17, 18-30 and 31-50 years), by type of physical activity and by intensity (as per fitness tracker default categorization)
  - The physical activities are categorized in the followings groups:
    - Exercises at intervals
    - Gymweights
    - Running
    - Swimming
    - Tapis roulant
    - Walk
    - General exercises: other types of physical activity identified by the fitness tracker that are not already included in the above-mentioned categories.
- To describe the observed population in terms of:
  - Number of patients who are adherent to World Health Organization (WHO) Guidelines (i.e., Global Recommendations on Physical Activity for Health) for the definition of physical activity.

The adherence to WHO guidelines will be derived considering the measures derived as described in Section 4.1.

A patient will be defined “adherent” to WHO guidelines if:

- 12-17 years old:

- MVPA minutes per day  $\geq$  60 minutes
- 18-50 years old:
  - Fairly active (moderate) minutes per week  $\geq$  150 minutes OR
  - Very active (vigorous) minutes per week  $\geq$  75 minutes OR
  - An equivalent combination of fairly and very active minutes (i.e. considering 1 fairly active minute as 0.5 very active minutes)

A subgroup analysis will be done by severity of the disease (see Section 4.4.5 for subgroup definition).

A patient who will result adherent to the WHO guidelines according to the previous definition will be define as an “active patient”, otherwise as a “sedentary patient”.

- Number, sites and types of bleeds occurring during routine clinical practice and reported at any occurrence via the electronic Patient-Reported Outcome (ePRO) application.
- Treatment regimen for haemophilia A (prophylaxis, preventative treatment before physical activity, treatment for any episode of bleeds), in terms of type of regimen (on demand vs. prophylaxis), product used and dose.
- Health-Related Quality of Life (HRQoL) and health status reported during routine clinical practice, measured using the European Quality of Life-5 Dimensions (EQ-5D-5L) score (adults/adolescents).

HRQoL will be evaluated at baseline, every 3 months, and at the end of the study).

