### **Bleeding and daily physical activity.**

The relationship between bleedings and physical activity (daily and by type) will be done as described in Section 4.4.1 but considering only data collected by the fitness tracker in the two days preceding the day in which the bleeding occurs.

For the relationship with daily physical activity, only data in the valid days will be considered. For each bleeding, the data collected in the two valid days before the bleeding will be summarized by the median. In case only one valid day is available, those values will be used to summarize the activity done before that bleeding.

All the activities recorded in the two days before the bleeding will be used regardless they occur in a valid day.

**To observe patients, on primary and secondary objectives, for additional 6 months if new therapies become commercially available for patients with Haemophilia A without inhibitors against FVIII, during the course of the study and if patient will start such treatments during the observation period.**

All the analysis proposed in sections 4.4.1 and 4.4.2 (except for the subgroup analyses) will be repeated by considering the start of any newly approved drug for haemophilia A during the study. See Section 4.4.4 for more details on this subgroup analysis.

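### The SAP's 'intense' activity label before a bleed only separates any moderate-to-vigorous activity from none, and it partly depends on how many days the tracker was worn

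*SAP*

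**What the plan says.** In SAP 4.4.2, under the treatment regimen for bleeding, treatment of bleeds is also to be analysed by how intense the patient's activity was in the two days before the bleed.

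- **Measure and summary:** "MVPA minutes will be summarized as median of the values recorded in the 2 valid days before the bleeding".
- **Cut:** "A median greater than 0 minutes will mean an intense physical activity".
- **One valid day:** "in case of only one valid day, that value will be used to summarize the physical activity preceding the bleeding".

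SAP 2.2 defines MVPA as fairly active plus very active minutes and states that "a valid day of monitoring is defined as at least 10 wearing hours per day". SAP 2.2.1 says what the two components mean when it sets the WHO criteria for adults: "Fairly active (moderate) minutes per week" and "Very active (vigorous) minutes per week".

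The rule has no minimum duration and no middle category, and it does not say where a bleed with no valid day goes. The later analysis of bleeding and daily physical activity uses the same two-day window and fallback ("In case only one valid day is available, those values will be used to summarize the activity done before that bleeding") but applies no cut and is not split by treatment. SAP 4.4.3 plans no sensitivity analysis.

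**The concern.** A table headed by intensity of activity should separate bleeds that followed intense activity from those that did not. A cut at zero on a measure that includes moderate minutes does something else: it isolates bleeds preceded by no moderate or vigorous activity at all and puts every other bleed under 'intense'. A reader could then conclude that bleeds after intense activity were treated more, less or differently, when the data show only a contrast between some activity and none.

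The rule also treats a one-day window and a two-day window as equivalent. With two valid days there are two chances of exceeding zero; with one there is a single chance. The two categories could therefore differ in tracker wear as well as in activity.

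**Working it through.** The SAP attaches no figure to this rule, so there is nothing to reproduce. The rule was applied as written.

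**1. What the cut separates.** The median of two values a and b is (a + b)/2, which exceeds 0 whenever either value does.

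- Daily MVPA of 1 and 0 minutes: (1 + 0)/2 = 0.5, above 0, so intense.
- Daily MVPA of 0 and 0 minutes: 0, so not intense.

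One fairly active minute on one day, with no vigorous activity, is enough. The one-minute example assumes recording by the minute. The documents do not state the smallest amount recorded, but the argument holds for whatever that amount is.

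**2. Same behaviour, different label.** Take 30 MVPA minutes two days before the bleed and 0 the day before.

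- Both days valid: (30 + 0)/2 = 15, intense.
- Only the earlier day valid: 30, intense.
- Only the later day valid: 0, not intense.

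**3. Size of the wear effect.** Let p be the chance that a valid day has any MVPA, taken as the same in one-day and two-day windows, and let ρ be the correlation between days. The documents give neither, so both are assumed and varied.

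- One valid day: chance of the label = p.
- Two valid days: chance = 1 − [(1 − p)² + ρp(1 − p)].
- Gap = (1 − ρ)p(1 − p), which is never negative.

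| p | One valid day | Two valid days, ρ = 0 | Gap, ρ = 0 | Gap, ρ = 0.3 | Gap, ρ = 0.6 |
|---|---|---|---|---|---|
| 0.1 | 10% | 19% | 9 points | 6.3 points | 3.6 points |
| 0.3 | 30% | 51% | 21 points | 14.7 points | 8.4 points |
| 0.5 | 50% | 75% | 25 points | 17.5 points | 10 points |
| 0.7 | 70% | 91% | 21 points | 14.7 points | 8.4 points |
| 0.9 | 90% | 99% | 9 points | 6.3 points | 3.6 points |

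**4. Would the SAP's WHO thresholds make a better cut?** For adults, 150 moderate minutes a week is 150/7 = 21.4 a day. Counting one very active minute as two fairly active ones, as SAP 2.2.1 does, the score is fairly active + 2 × very active minutes per valid day.

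- *Wear:* 30 and 0 fairly active minutes give 15 with two valid days (below 21.4), but 30 (above) or 0 (below) with one. The label still changes with wear.
- *Intensity:* 20 very active minutes on one of two days score 2 × 20/2 = 20, below the cut. By contrast, 22 fairly active minutes a day with no vigorous activity score 22, above it.
- *Adolescents:* 110 very active minutes on one day and 0 on the other average 55, below the 60-minute criterion.

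These thresholds measure habitual volume. They do not identify intense activity in a two-day window, and they leave the wear problem in place.

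**The case against.** The best defence is that little rests on this table. It is one descriptive breakdown of a secondary endpoint, it has no planned test or interval, and the cut is stated openly. The separate analysis of activity before bleeds already summarises fairly active, very active, cardio and peak minutes without a cut, and every bleed and its treatment will be listed. All of this stands and keeps the severity low. It does not make 'intense' an accurate name, and nothing else planned sets vigorous activity against bleed treatment.

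The wear effect is also unquantified: p and the between-day correlation are unknown, and the gap shrinks as the correlation rises. That is why only a range is given.

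Three stronger readings are tempting but are not supported:

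- **That the SAP contradicts itself by calling a sedentary patient's activity intense.** Active or sedentary is a patient-level class based on WHO adherence; the intensity label belongs to one bleed and two days. A habitually sedentary patient can be intensely active before a particular bleed. Ratios of the zero cut to the WHO thresholds mix these two levels.
- **That the analysis will give a wrong conclusion about treatment.** The plan draws no such conclusion. One drawn from this table would be unsupported, which is a weaker charge.
- **That the 'not intense' group reflects illness or rest after an earlier bleed.** This is possible, but nothing in the documents shows it.

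**Conclusion.** The rule is wrong as written, with low stakes. It follows from the SAP's own definitions that the split is any MVPA against none, whatever the tracker's smallest recorded amount. It also follows that, with the same daily chance of MVPA, a bleed with two valid days is at least as likely to be labelled intense as a bleed with one. The size of that effect is unknown: 9 to 25 percentage points for p from 0.1 to 0.9 with independent days, and 3.6 to 10 points at a correlation of 0.6, all on assumed inputs.

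The wear result takes the window to be the two calendar days before the bleed, which is the reading under which a one-day fallback makes sense. The primary endpoint is not affected.

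**What to change.** In SAP 4.4.2:

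1. Rename the split 'any MVPA vs no MVPA in the two days before the bleed' and drop the word 'intense'.
2. Beside it, summarise very active (vigorous) minutes per valid day as a continuous value by bleed treatment.
3. Show the number of valid days in each category, and repeat the table for bleeds with two valid days. This count will also expose bleeds with no valid day, which the rule does not place.

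Do not recode to the WHO thresholds, for the reasons in step 4 of the working.

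The change uses data already collected. It costs a few lines of SAP text and one more small table, and the two-valid-day version will contain fewer bleeds.

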#### **Health-Related Quality of Life (HRQoL) and health status reported during routine clinical practice, measured using the European Quality of Life-5 Dimensions (EQ-5D-5L) score**

The EQ-5D-5L score will be analyzed at baseline and monthly up to the end of the observational period. The month will be derived as: rounded[(reference date – baseline date + 1) /30.4375].

The EQ-5D Index Utility Score as well as the EQ VAS Score will be analyzed according to their continuous nature. The change from baseline will also be shown. The 95%CIs for the mean and for the mean change from the baseline will also be calculated.

Moreover, the score related to each dimension (mobility, selfcare, usual activity, pain/discomfort and anxiety/depression) will be analyzed according to its categorical nature in the overall sample. Number and proportion of patients in each category will be displayed (No problems, Slight problems, Moderate problems, Severe problems, Extreme problems).

Data will also be summarized:

- by start of any newly approved drug for haemophilia (see Section 4.4.4 for subgroup definition).
- by COVID-19 period (see Section 4.4.4 for subgroup definition).
- by month through the entire observational period to observe the impact of COVID-19.

In case of more than 1 value for each subject in each period, the continuous variable will be replaced by using the mean of the value for each subjects, the qualitative variables (e.g. the score domain) will be replaced by the worst value.

Other subgroup analyzes: frequency of physical activity, severity of the disease (see Section 4.4.4 for subgroup definition).

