Additionally, patients (or patient's legally authorized representative) will be reminded on a monthly basis to report via their ePRO application whether a bleed has occurred and whether treatment for a bleed or treatment to prevent a further bleed has been given. When a bleed occurs, the patient (or patient's legally authorized representative) will be required to report bleed information, including site of bleed, type of bleed, time of each individual bleed (date, time of start and time of end), symptoms of bleed, and treatment for bleed.

Health status will be captured in ePRO via the visual analogue scale (VAS) component of the EQ-5D-5L at baseline, every 3 months and at the end of study.

Physical activity will be measured daily by wearing a fitness tracker continuously during study participation. Patients will be daily reminded to wear the device. A valid day of monitoring is defined as at least 10 wear hours per day. Wear time will be derived though data collected by the fitness tracker.

The reason for the use of coagulation products (e.g., bleeding, prophylaxis, pain, etc.) will be documented by Investigator in source data and reported in the e-CRF. The reason for the use of coagulation products for bleeding treatment, including agent, start time, dose, route of administration, and number of infusions needed to treat the bleed, will be recorded by patients in the ePRO application and will be then transmitted to the eCRF.

Therapy will be recorded by the investigator at baseline visit and it will afterwards be confirmed by the patient in ePRO application. If there are changes to the assigned therapy, the patient will enter therapy variations in ePRO (*e.g.*, dose, frequency, drug name etc.) and data will be then transmitted to the eCRF.

Demographics and results from physical examinations, and vital sign assessments, will only be collected if available from routine clinical practice. No additional diagnostic or monitoring procedures will be applied to the patients outside of routine clinical practice.

Start Date of Study:

The study start date will be the date of the signing of informed consent of the first patient (or caregiver). The planned start date is October 2019.

End of Study:

The end of the study will be the date on which the last patient performs the last visit, this is expected when:

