The EQ-5D-5L is a standardized measure of health status developed by the EuroQol Group in order to provide a simple, generic measure of health for clinical and economic appraisal (*Herdman et al. 2011*). The EQ-5D-5L (Appendix 5) includes five levels of severity in each of the five EuroQol-5D dimensions and the EQ VAS. The descriptive system comprises 5 dimensions (mobility, self-care, usual activities, pain/discomfort, anxiety/depression), each dimension having 5 levels (no problems, slight problems, moderate problems, severe problems, and extreme problems). The EQ VAS records the respondent's self-rated health on a vertical, visual analogue scale numbered from 0 to 100 with endpoints labelled 'the best health you can imagine' and 'the worst health you can imagine'.

The EQ-5D-5L will be completed at baseline, every three months and at the end of the study, as well as at each episode of bleeding.

VAS for pain (via ePRO)

The intensity of pain in the main joints (elbow, knee, ankle) will be evaluated (at baseline, every month and at the end of the study, as well as at each bleeding episode) by means of a 100 mm VAS and will be recorded through ePRO application.

The VAS is an instrument that measures the amount of pain that a patient feels across a continuum from none to an extreme amount of pain.

Operationally a VAS is usually a horizontal line (see example below), 100 mm in length, anchored by word descriptors at each end, where the left extreme means "No pain = 0" while the right extreme means "Worst Pain Imaginable = 100".

After sitting for 15 minutes, the extent of pain at the injury site will be evaluated in answer to the question: "How would you describe your injury related pain right now?"

Patients will mark on the line the point that they feel representing their perceived pain. The VAS score is the distance (in millimeters) from the left end of the line to the point where the patient's mark crossed the line.

It has been demonstrated that the measurement of the response VAS scale collected on paper and by electronic administration, using BYOD or a site-provisioned device, are equivalent. In addition, there is no evidence of a difference in measurement properties of each response scale type across different screen sizes of devices (*Bill Byrom et al. 2018*)

Caregiver burden

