- Bleeding and treatments for bleeds will be reported in a continuous manner, during study participation. Patients will be prompted electronically on a monthly basis to report any bleeds. In case of bleeds, patients will report bleed information, including site of bleed, type of bleed, time of each individual bleed (date, start time and end time), symptoms of bleed, treatment for bleed and health status information. The following information on treatments for bleeds will be reported: agent, start time, dose, route of administration, and number of infusions needed to treat the bleed. At baseline, information about any bleedings which occurred in the previous 24 weeks will be collected.
- ⁸ VAS for pain will be evaluated at baseline, monthly and at the end of study.
- ⁹ EQ-5D-5L for pain will be evaluated at baseline, every 3 months and at the end of study
- ¹⁰ Evaluated at baseline, monthly and at the end of the study
- ¹¹ HJHS will be evaluated at baseline, at 6 months and at the end of the study. HJHS will be also performed at the time of start of treatment with any newly approved drugs, and at 6 months following the start of treatment drugs.

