### **Amendment 2.0: 15 July 2022:**

In section 2.2.1 the types of physical activities identified by the fitness tracker have been listed.

In Section 4.1.4, the definition of SWITCH population has been added along with the classification of subjects who switch to a replacement or non-replacement therapy.

In Section 4.2.3, the time to discontinuation will be analyzed even if less than 30% of subjects will discontinue the study in order to provide an estimate of the median follow-up time.

In Section 4.4.2, the following changes have been done:

- Treatment regimen for bleeding: number and proportion of bleeding with adherence to treatment regimen in the week preceding the bleeding will be shown.
- HRQoL measured using the EQ-5D-5L will be analyzed monthly instead of every 3 months, deriving the timepoint from the date in which the questionnaire is recorded in the ePRO.
- Annualized Bleeding Rate: Number and proportion of subjects with at least one bleeding will be also shown.
- The analysis to explore the relationship between bleedings and physical activity has been explained better.

In Section 4.4.4, the following changes have been done:

- the definition of subgroups accordingly to the start of any newly approved drug for haemophilia has been updated.
- the analysis by month to observe the impact of COVID-19 has been added.

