## 8.

## **APPENDIX 2: SCHEDULE OF ASSESSMENTS**

Assessments and study visits will be performed as listed in the Table 2.

Visits at the clinic will be performed approximately every three months, but some degree of flexibility (e.g.,  $\pm$  1 month or higher) will be considered according to Investigator's judgment and local clinical practice.

During the study, HRQoL, health status, joint health status will be reported on a pre-determined frequency for 12 months. Physical activity data will be collected daily using a fitness tracker.

Additionally, patients (or patient's legally authorized representative) will be reminded on a monthly basis to report via their ePRO application whether a bleed has occurred and whether treatment for a bleed or treatment to prevent a further bleed has been given. When a bleed occurs, the patient (or patient's legally authorized representative) will be required to report bleed information, including site of bleed, type of bleed, time of each individual bleed (date, time of start and time of end), symptoms of bleed, and treatment for bleed.

Health status will be captured in ePRO via the visual analogue scale (VAS) component of the EQ-5D-5L at baseline, every 12 weeks and at the end of study.

Physical activity will be measured daily by wearing a fitness tracker continuously during study participation. Patients will be daily reminded to wear the device. A valid day of monitoring is defined as at least 10 wear hours per day. Wear time will be derived through data collected by the fitness tracker.

The reason for the use of coagulation products (e.g., bleeding, prophylaxis, pain, etc.) will be documented by the Investigator in the source data and reported in the e-CRF. The reason for the use of coagulation products for bleeding treatment, including agent, start time, dose, route of administration, and number of infusions needed to treat the bleed, will be recorded by patients in the ePRO application and will be then transmitted to the eCRF.

Therapy will be recorded by the investigator at baseline visit and it will afterwards be confirmed by the patient in ePRO application. If there are changes to the assigned therapy, the patient will enter therapy variations in ePRO (e.g., dose, frequency, drug name etc.) and data will be then transmitted to the eCRF.

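### The worst-value rule for EQ-5D dimensions makes a period with more forms look worse, and the EQ-5D-5L collection passages need reconciling

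*SAP*

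**What the plan says.** **Analysis.** SAP 4.4.2 (HRQoL) says: "The EQ-5D-5L score will be analyzed at baseline and monthly up to the end of the observational period". The month is the rounded value of (date − baseline + 1)/30.4375. The summary of SAP Amendment 2.0 shows that this was deliberate: "HRQoL measured using the EQ-5D-5L will be analyzed monthly instead of every 3 months", with the time point taken from the recording date. The same part of 4.4.2 plans summaries before and after the start of a newly approved drug, by COVID-19 period and by month. Where a patient has several values in a period, continuous scores are averaged and each dimension takes its worst level. SAP 4.4.4 defines the lockdown windows as 1 March to 4 May 2020 and 13 October to 31 December 2020, and plans a comparison with the time outside them. SAP 4.7 imputes nothing.

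**Collection.** The passages do not agree:
- SAP 2.2.1: "HRQoL will be evaluated at baseline, every 3 months, and at the end of the study". The objectives in the protocol synopsis and Protocol 5.2.1 give the same interval.
- Protocol Appendix 2, footnote 9 (repeated under SAP Table 2): "EQ-5D-5L for pain will be evaluated at baseline, every 3 months and at the end of study".
- EQ VAS in Protocol 6.1.1: "component of the EQ-5D-5L at baseline, every 3 months and at the end of study". EQ VAS in SAP Appendix 2: "component of the EQ-5D-5L at baseline, every 12 weeks and at the end of study".
- Protocol 6.4.1 (HRQoL) adds a bleed trigger: "every three months and at the end of the study, as well as at each episode of bleeding". Footnote 7 of the schedule asks, at a bleed, for "symptoms of bleed, treatment for bleed and health status information". SAP 2.2.1 and footnote 9 mention no form at a bleed.

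No passage schedules EQ-5D-5L monthly.

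**The concern.** The worst of several forms can only equal or exceed the worst of one. If two periods hold different numbers of forms, the rule creates a difference between them even when health is unchanged. The lockdown windows are shorter than the interval between forms, so the counts differ systematically in a comparison that the SAP plans. If lockdown did harm quality of life, the rule would work against seeing it. The index score and EQ VAS are averaged within a period and do not have this fault, so one table could show a stable index beside dimensions that look worse outside lockdown.

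The schedule is a second, separate matter. The SAP does not make clear which forms feed the tables. On a 3-monthly schedule, most monthly columns would describe whoever happened to have an off-schedule form, not the cohort. Quality of life is a secondary outcome but is named in the study title.

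**Working it through.** The plan gives no figure for this point, so there is none to reproduce.

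**1. Forms per period.** On-time 3-monthly forms fall at days 0, 91, 183, 274 and 365, with gaps of 91 or 92 days.
- First window: 31 + 30 + 4 = 65 days. Second window: 19 + 30 + 31 = 80 days.
- Both are shorter than the smallest gap, so each holds 0 or 1 form per patient.
- Five forms less at most two leaves 3 to 5 outside lockdown. Running every enrolment date from 1 October 2019 (planned start October 2019) to 30 April 2021 (end of enrolment, SAP 2.3.1) gives the same counts.

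This needs no bleed-time forms.

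**2. Effect of the worst-value rule.** Let p be the chance that one form shows a moderate or worse level, the same in every period. The documents give no p, so 10%, 20% and 30% are assumed.
- Independent forms: P = 1 − (1 − p)^k. At p = 0.2, k = 3 gives 1 − 0.8³ = 0.488 and k = 5 gives 1 − 0.8⁵ = 0.672. Independence within a patient is an upper bound.
- Correlated forms (beta-binomial, assumed correlation 0.7): a + b = 1/0.7 − 1 = 0.4286. At p = 0.2, a = 0.0857 and b = 0.3429. P(none in k) is the product of (b + i)/(a + b + i) for i = 0 to k − 1. For k = 3: 0.800 × 0.940 × 0.9647 = 0.7255, so P = 0.27. For k = 5, multiply further by 0.975 × 0.9806 to get 0.6936, so P = 0.31.

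| Assumed p | 1 form | 3–5 forms, correlation 0.7 | 3–5 forms, independent (upper bound) |
|---|---|---|---|
| 10% | 10% | 14–16% | 27–41% |
| 20% | 20% | 27–31% | 49–67% |
| 30% | 30% | 40–44% | 66–83% |

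A per-patient proportion has expectation k·p/k = p for any k and any correlation, so it does not have this fault.

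**3. Before and after a switch.** Scheduled forms, without a form at drug start:
- Start in months 0–3: 1 before (month 0), 4 after (months 3, 6, 9, 12).
- Start in months 3–6: 2 before, 3 after.
- Start in months 6–12: 3 to 5 before. After the start there are 2 (3 and 6 months post-start), or 3 if the ePRO record at drug start (Protocol 6.4.1) is counted. This assumes that the post-start visits replace the remaining regular ones, which the schedule does not state.

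**4. Month mapping.** (91 + 1)/30.4375 = 3.02; (183 + 1)/30.4375 = 6.05; (274 + 1)/30.4375 = 9.03; (365 + 1)/30.4375 = 12.02. These give months 3, 6, 9 and 12. Forms every 12 weeks (days 84, 168, 252, 336) give 2.79, 5.55, 8.31 and 11.07, which are months 3, 6, 8 and 11. On the 3-monthly schedule, 8 of the 12 post-baseline months contain no on-time form. They are filled by displaced forms, early-termination forms, new-drug forms and, if the trigger operated, bleed-time forms.

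**The case against.** The strongest defence is that the monthly grid is a documented, date-based choice. Visit timing is not mandatory (Protocol 6.4.1), and binning by actual date is a reasonable way to handle irregular forms. It also serves the month-by-month COVID-19 view. That stands: a monthly grid does not itself contradict a 3-monthly schedule. If forms are on time and there is no bleed trigger, the off-schedule months are close to empty and the reported n shows it. The results are descriptive, listings are provided, and the primary endpoints are untouched.

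A reader might go further in three ways that the documents do not support:
- That off-schedule months are dominated by bleeding patients. The documents give no bleed rate, no completion rate for bleed-time forms and no score at a bleed. They do not show whether the application issued EQ-5D-5L at bleeds. Visit flexibility concerns clinic visits, while the form is completed on the patient's own device.
- That the period before a drug switch always looks worse. The SWITCH population in SAP 4.1.4 covers any start during observation, and the counts in step 3 reverse for starts in months 0–6 and can tie for starts in months 6–9.
- That the distortion is as large as the independent-forms column. One patient's forms are likely to be correlated, so that column is only a ceiling.

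Averaging monthly and bleed-time pain VAS records within a month is also a legitimate summary, provided it is labelled as one.

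**Conclusion.** The worst-value rule should be changed. Its direction in the lockdown comparison follows from the documents alone, given on-time 3-monthly forms: at most 1 scheduled form inside each window against 3 to 5 outside, so the dimensions look worse outside lockdown with no real difference. The size rests on assumptions. At 20% per form and correlation 0.7 it is 20% against about 27% to 31%, with 49% to 67% as the upper bound. The switch summary depends on form counts in the same way, but its direction varies with the switch month.

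The collection passages conflict on the EQ VAS interval and on forms at bleeds and must be reconciled. The monthly tables need clearer labelling and a scheduled-form counterpart; how far they mislead cannot be derived from the documents. Only descriptive secondary results are affected, so this is a correction worth making and not a threat to the study's main result.

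**What to change.** - For period summaries of EQ-5D dimensions, replace the worst value by each patient's proportion of scheduled records in each category, averaged over patients, so that each patient counts once.
- State one EQ-5D-5L and EQ VAS schedule across the protocol synopsis, Protocol 5.2.1, 6.1.1, 6.4.1 and Appendix 2, and SAP 2.2.1, 4.4.2 and Appendix 2. State whether EQ-5D-5L was collected at bleeds.
- For time-course and change-from-baseline summaries, use scheduled forms in windows around the reconciled schedule. If it is 3-monthly, the midpoints between target days (45.5, 137, 228.5 and 319.5) give days 46–137, 138–228, 229–319 and 320 onward.
- Report bleed-time EQ-5D-5L and pain VAS records separately, identified by a trigger label or, failing that, by matching to recorded bleed dates.
- If the monthly all-records table is kept for the COVID-19 view, label it so and show the number of bleed-time forms in each month.

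The work is SAP wording and perhaps one date-matching step, since bleed dates are already collected. The costs are fewer EQ-5D-5L time points, some misclassification if forms must be matched by date, and some patients with no scheduled form in a lockdown window. With forms about 91.3 days apart, coverage among patients observed throughout a window is about 65/91.3 = 71% for the first and 80/91.3 = 88% for the second.
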